8.2. Adverse Events

8.2.1. Adverse Event Definitions

A TEAE is any AE either reported for the first time or worsening of a pre-existing event after first administration of study drug. Analysis of AEs (as discussed below) will be limited to TEAEs, but data listings will include all AEs regardless of their timing in relation to study drug administration.

Adverse events will be tabulated by MedDRA PT and SOC. Severity of AEs will be graded using the NCI CTCAE. The CTCAE v4.03 (2010) is used for this study. The CTCAE reporting guidelines and grading details are available on the Cancer Therapy Evaluation Program website.

The subset of AEs considered by the investigator to be related to study drug will be considered to be treatment-related AEs. The incidence of AEs and treatment-related AEs will be tabulated. Serious AEs (SAEs) will also be tabulated.

Any missing onset date, causality, or severity must be queried for resolution. Unresolved missing causality and severity will be handled according to the following rules:

- An unresolved missing causality will be considered treatment-related.
- An unresolved missing severity will be identified as an unknown severity.

For purposes of analysis, all AEs will be considered TEAEs unless the AE can unequivocally be defined as not treatment-emergent.

8.2.2. Adverse Event Summaries

An overall summary of AEs will include the following:

- Number (%) of participants reporting any TEAEs
- Number (%) of participants reporting any SAEs
- Number (%) of participants reporting any Grade 3 or 4 TEAEs
- Number (%) of participants reporting any treatment-related TEAEs
- Number (%) of participants who temporarily interrupted study treatment because of TEAEs
- Number (%) of participants who permanently discontinued study treatment because of TEAEs
- Number (%) of participants who had a TEAE leading to death

The following summaries will be produced by MedDRA term (if 2 or fewer participants appear in a table, a listing may be appropriate):

- Summary of TEAEs by SOC and PT
- Summary of TEAEs by PT in decreasing order of frequency
- Summary of TEAEs by SOC, PT, and maximum severity
- Summary of treatment-related AEs by SOC and PT
- Summary of treatment-related AEs by PT in decreasing order of frequency
- Summary of treatment-related AEs by SOC, PT, and maximum severity
- Summary of Grade 3 or 4 AEs by SOC and PT
- Summary of Grade 3 or 4 treatment-related AEs by SOC and PT
- Summary of TEAEs leading to death by SOC and PT
- Summary of treatment-emergent SAEs by SOC and PT
- Summary of treatment-emergent SAEs by PT in descending order of frequency
- Summary of treatment-related SAEs by SOC and PT
- Summary of TEAEs leading to dose interruption by SOC and PT
- Summary of TEAEs leading to discontinuation of treatment by SOC and PT
- Summary of nonserious TEAEs by SOC and PT

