10.4.2. Safety Analyses

Safety analyses will be conducted for the FAS population. Adverse events will be coded by the MedDRA dictionary, and TEAE (ie, AEs reported for the first time or worsening of a pre-existing event after first dose of study drug) will be tabulated by preferred term and system organ class for all events, related events, and events of Grade 3 or higher. Quantitative safety variables and their changes from baseline (laboratory, vital signs, etc) will be summarized with descriptive statistics. Clinically notable abnormal values will be flagged and tabulated based on predefined criteria.

The clinical laboratory data will be analyzed using summary statistics; no formal treatment group comparisons are planned. In addition, distributions of key laboratory parameters may be plotted over time; these values will also be classified into CTCAE toxicity grades and tabulated.

Descriptive statistics and mean change from baseline will be determined for vital signs at each assessment time. Vital sign results will be reviewed for clinically notable abnormalities.

[REDACTED]

[REDACTED]

The secondary endpoint of change and percent change from baseline in salivary CXCL13 levels at Week 4 and 12 will be determined from saliva samples for each participant.

All analyses will be conducted by Incyte Corporation (Wilmington, DE) or Incyte's designee, and information regarding handling/shipping of specimens will be provided in the Laboratory Manual.

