3.2 Adverse Events		
3.2.1	Overall Summary of Treatment-Emergent Adverse Events	FAS
3.2.2	Summary of Treatment-Emergent Adverse Events by MedDRA System Organ Class and Preferred Term	FAS
3.2.3	Summary of Treatment-Emergent Adverse Events by MedDRA Preferred Term in Decreasing Order of Frequency	FAS
3.2.4	Summary of Treatment-Emergent Adverse Events by MedDRA System Organ Class, Preferred Term, and Maximum Severity	FAS
3.2.5	Summary of Grade 3 or Higher Treatment-Emergent Adverse Events by MedDRA System Organ Class and Preferred Term	FAS
3.2.6	Summary of Treatment-Related Adverse Events by MedDRA System Organ Class and Preferred Term	FAS
3.2.7	Summary of Treatment-Related Adverse Events by MedDRA Preferred Term in Decreasing Order of Frequency	FAS
3.2.8	Summary of Treatment-Related Adverse Events by MedDRA System Organ Class, Preferred Term, and Maximum Severity	FAS
3.2.9	Summary of Grade 3 or Higher Treatment-Related Treatment-Emergent Adverse Events by MedDRA Preferred Term	FAS
3.2.10	Summary of Treatment-Emergent Adverse Events Leading to Death by MedDRA System Organ Class and Preferred Term	FAS
3.2.11	Summary of Treatment-Emergent Serious Adverse Events by MedDRA System Organ Class and Preferred Term	FAS
3.2.12	Summary of Treatment-Emergent Serious Adverse Events by MedDRA Preferred Term in Decreasing Order of Frequency	FAS
3.2.13	Summary of Treatment-Related Serious Adverse Events by MedDRA System Organ Class and Preferred Term	FAS
3.2.14	Summary of Treatment-Emergent Adverse Events Leading to Dose Interruption by MedDRA System Organ Class and Preferred Term	FAS
3.2.15	Summary of Treatment-Emergent Adverse Events Leading to Discontinuation of Treatment by MedDRA System Organ Class and Preferred Term	FAS
3.2.16	Summary of Nonserious Treatment-Emergent Adverse Events by MedDRA System Organ Class and Preferred Term ^a	FAS

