3.5 ECG		
3.5.1	Summary of PR Interval (msec) From 12-Lead ECG	FAS
3.5.2	Summary of RR Interval (msec) From 12-Lead ECG	FAS
3.5.3	Summary of QT Interval (msec) From 12-Lead ECG	FAS
3.5.4	Summary of QRS Interval (msec) From 12-Lead ECG	FAS
3.5.5	Summary of QTcB Interval (msec) From 12-Lead ECG	FAS
3.5.6	Summary of QTcF Interval (msec) From 12-Lead ECG	FAS
3.5.7	Summary of Heart Rate (bpm) From 12-Lead ECG	FAS
3.5.8	Summary of Outliers of QT, QTcB, and QTcF Interval Value (ms) From 12-Lead ECG	FAS
3.5.9	Summary of Clinically Significant ECG Abnormality	FAS

Listings

Listing No.	Title
Demographic and Baseline Characteristics	
2.1.1	Participant Enrollment and Disposition Status
2.1.2	Participant Inclusion and Exclusion Criteria Violations
2.2.1	Protocol Deviations
2.4.1	Demographic
2.4.2	Baseline Disease Characteristics
2.4.3	General Medical History
2.4.4	Prior and Concomitant Medications
2.4.5	Prior Medications for Sjögren's syndrome
2.5.1	Study Drug Compliance
Efficacy	
2.6.1	SGUS Score
2.6.2	Stimulated and unstimulated salivary flow
2.6.3	ESSDAI
2.6.4	ESSPRI
2.6.5	Symptom scores for dryness of eyes, mouth, and vagina
2.6.6	PGIC category
2.6.7	PROMIS Fatigue
2.6.8	FSFI
2.6.9	EQ-5D
Adverse Events and Exposure	
2.7.1	Study Drug Administration
2.7.2	Adverse Events
2.7.3	Serious Adverse Events
2.7.4	Grade 3 and Higher Adverse Events
2.7.5	Adverse Events Leading to Death
2.7.6	Treatment-Related Adverse Events
2.7.8	Adverse Events Leading to Dose Interruption
2.7.9	Adverse Events Leading to Discontinuation

Listing No.	Title
Laboratory Data	
2.8.1	Clinical Laboratory Values – Hematology
2.8.2	Clinical Laboratory Values – Serum Chemistry
2.8.3	Abnormal Clinical Laboratory Values – Hematology
2.8.4	Abnormal Clinical Laboratory Values – Serum Chemistry
Vital Signs	
2.9.1	Vital Signs
2.9.2	Abnormal Vital Sign Values
2.9.3	Alert Vital Sign Values
ECG	
2.10.1	12-Lead ECG Values
2.10.2	Abnormal 12-Lead ECG Values
2.10.3	Alert 12-Lead ECG Values

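### SAP 8.2.2 stops its severe-event summaries at Grade 4, whereas Protocol 10.4.2 and the SAP's own table list include Grade 5, so a participant whose only severe event is fatal would be missing from those counts (minor)

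*SAP*

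**What the plan says.** SAP 8.2.2 has three lines on severe events, all with the same grade range:

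- In the overall summary: "Number (%) of participants reporting any Grade 3 or 4 TEAEs".
- In the by-term list, for all events: "Summary of Grade 3 or 4 AEs by SOC and PT".
- In the by-term list, for treatment-related events: "Summary of Grade 3 or 4 treatment-related AEs by SOC and PT".

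Protocol 10.4.2 says that treatment-emergent events "will be tabulated by preferred term and system organ class for all events, related events, and events of Grade 3 or higher".

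SAP Appendix A has the same lower bound as the Protocol and no upper limit. Table 3.2.5 is titled "Summary of Grade 3 or Higher Treatment-Emergent Adverse Events by MedDRA System Organ Class and Preferred Term", Table 3.2.9 is titled "Summary of Grade 3 or Higher Treatment-Related Treatment-Emergent Adverse Events by MedDRA Preferred Term", and Listing 2.7.4 is titled "Grade 3 and Higher Adverse Events". The title of Table 3.2.1, the overall summary, names no grade.

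Protocol 9.3 grades severity from 1 to 5 under CTCAE v4.03, with Grade 5 meaning fatal. SAP 8.2.1 uses the same CTCAE version. SAP 10.1 gives changes to Protocol-defined analyses as not applicable.

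**The concern.** The body of the SAP and its table list give different definitions of a severe event, and the difference is the most severe grade on the scale. Appendix A describes its list and shells as a guideline, so it does not clearly override 8.2.2. One programmer could build the tables to Grade 4 from the body text, another could build them to Grade 5 from the titles, and both could say they followed the SAP.

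Two things are at stake. A participant whose only severe event is fatal would be absent from counts that a reader takes to cover all severe events. If the overall row follows 8.2.2 while Table 3.2.5 follows its title, one report could also give two different numbers of participants with severe treatment-emergent events. Safety and tolerability, including severity of adverse events, is a secondary objective, so these are planned results.

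**Working it through.** **Inputs.** The grade ranges come from SAP 8.2.2, Protocol 10.4.2 and SAP Appendix A. The meaning of Grade 5 and the recording rule come from Protocol 9.3. The planned number, about 12, comes from SAP 3.3 and Protocol 10.1.

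**The plan's own figure.** The only probability the documents state is the chance of seeing at least one event of interest among 12 participants at a 20% rate. It is 1 − 0.8^12 = 0.931, which agrees with the stated value of more than 90%. The present point does not depend on it.

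**Side by side.**

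| SAP 8.2.2 line | Grades in 8.2.2 | Counterpart | Grades in counterpart | Conflict |
|---|---|---|---|---|
| All events, by term | 3–4 | Protocol 10.4.2; Table 3.2.5 | 3–5 | Direct, with both |
| Treatment-related, by term | 3–4 | Table 3.2.9 | 3–5 | With Table 3.2.9 only; the Protocol lists related events and severe events separately and does not ask for the combination |
| Overall summary row | 3–4 | Table 3.2.1 | none named | No stated conflict, but its count can differ from Table 3.2.5 |

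The layout of the treatment-related table differs too: 8.2.2 gives it by system organ class and preferred term, and Table 3.2.9 by preferred term only.

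**Who is affected.** The two definitions give different counts only for a participant who has a Grade 5 treatment-emergent event and no recorded Grade 3 or 4 one (for Table 3.2.9, counting related events only). Protocol 9.3 records each change in severity as a separate event. A participant whose event was recorded at Grade 3 or 4 before it became fatal is therefore counted either way.

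**Size.** Assume 12 treated participants, one of whom has a fatal event as the only severe event. Let k be the number of other participants with a Grade 3 or 4 event. The reported proportion is k/12 under Grade 3 or 4 and (k + 1)/12 under Grade 3 or higher.

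| k | Grade 3 or 4 | Grade 3 or higher |
|---|---|---|
| 0 | 0/12 = 0.0% | 1/12 = 8.3% |
| 1 | 1/12 = 8.3% | 2/12 = 16.7% |
| 2 | 2/12 = 16.7% | 3/12 = 25.0% |

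The difference is always 1/12 = 8.3 percentage points per such participant. With none, it is zero.

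**Where the death would still appear.** SAP 8.2.2 has an overall row and a by-term table for events leading to death, maximum-severity tables for all and for treatment-related events, and serious-event tables. Listings 2.7.4 and 2.7.5 in Appendix A cover severe events and events leading to death.

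**The case against.** The strongest reply is that nothing is hidden. The overall summary has its own row for events leading to death, so a Grade 3 or 4 row beside it can be read as written. Every death is also in the other tables and listings named above. SAP 8.1 and 8.2.2 allow sparse tables to be replaced by listings, and the severe-event listing already includes Grade 5. All analyses are exploratory and no tests are planned. This stands, and it limits the point to a minor one. It does not remove the mismatch: the by-term line for all events departs from the Protocol without being declared, and the body of the SAP disagrees with its own table titles.

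A reader might infer more than the documents support:

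- *That the Protocol contradicts all three lines.* It sets a grade range only for tabulation by preferred term and system organ class. It gives none for an overall row and asks for no table of related severe events.
- *That the overall summary would disagree with Table 3.2.9.* The overall summary has no row for treatment-related severe events, so there is nothing to compare with that table.
- *That the by-term lines wrongly admit events that are not treatment-emergent, because they say AEs and Table 3.2.5 says treatment-emergent.* SAP 8.2.1 already limits the analysis of adverse events to treatment-emergent ones, so no change is needed there.

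**Conclusion.** The inconsistency is real and minor. As written, the three severe-event summaries in SAP 8.2.2 leave out Grade 5. The all-event by-term line conflicts with Protocol 10.4.2 and Table 3.2.5, the treatment-related line conflicts with Table 3.2.9, and the overall row can differ from Table 3.2.5. SAP 10.1 declares no departure, and the documents give no reason for the narrower range.

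The 8.3-point figure assumes that 12 participants are treated and that the tables are programmed from the body text, and it applies per participant whose only severe treatment-emergent event is fatal. It illustrates the size of the effect and does not forecast that such a case will occur. The documents do not support reading this as a loss of deaths from the report. The omission is confined to the severe-event counts.

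**What to change.** In SAP 8.2.2, replace Grade 3 or 4 with Grade 3 or higher in all three lines: the overall row, the all-event by-term table and the treatment-related by-term table. In the same edit, choose one layout for the treatment-related table and use it in both 8.2.2 and Table 3.2.9.

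The cost is a few words in one section and possibly one table title. Data collection, sample size and methods are unaffected. The edit is best made before the tables are programmed.

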8.3. Clinical Laboratory Tests

8.3.1. Laboratory Value Definitions

Laboratory values, change from baseline values, and percentage change from baseline values will be summarized descriptively by visit. Baseline values will be determined using the nonmissing values collected before the first administration, prioritizing scheduled assessments over unscheduled visits. For baseline laboratory candidates with the same date and time in the same priority category, additional rules may be provided after consultation with the medical monitor to delineate which value will be defined as baseline.

Laboratory test values outside the normal range will be assessed for severity based on CTCAE grade or similar criteria where clinical intervention is required for CTCAE grading. The incidence of abnormal laboratory values and shift tables relative to baseline will be tabulated.

8.3.2. Laboratory Value Summaries

All test results and associated normal ranges from central laboratories will be reported in SI units. All tests with numeric values will have a unique unit per test.

When there are multiple laboratory nonmissing values for a participant's particular test at a scheduled postbaseline visit, use the smallest laboratory sequence number to identify the record.

Laboratory hematology and serum chemistry parameters identified in Protocol Table 10 will be summarized. Numeric laboratory values will be summarized descriptively in SI units, and non-numeric test values will be tabulated when necessary. In addition, box-and-whisker plots may be provided for some tests if applicable.

For test results that will be summarized with available normal ranges, the number and percentage of participants with the laboratory values being low, normal, high, and missing will be tabulated for each test and each visit.

Shift tables will be presented showing change in CTCAE grade from baseline to worst grade postbaseline. The denominator for the percentage calculation will be the number of participants in the baseline category.

8.4. Vital Signs

Values at each scheduled visit, change, and percentage change from baseline for vital signs, including systolic blood pressure, diastolic blood pressure, pulse, respiratory rate, and body temperature will be summarized descriptively.

Criteria for clinically notable vital sign abnormalities are defined in [Table 2](#). The abnormal values for participants exhibiting clinically notable vital sign abnormalities will be listed. Alert vital signs are defined as an absolute value outside the defined range and percentage change from baseline outside (-25%, 25%). The abnormal values for participants exhibiting alert vital sign abnormalities will be listed.

Table 2: Criteria for Clinically Notable Vital Sign Abnormalities

Parameter	High Threshold	Low Threshold
Systolic blood pressure	> 155 mmHg	< 85 mmHg
Diastolic blood pressure	> 100 mmHg	< 40 mmHg
Pulse	> 100 bpm	< 45 bpm
Respiratory rate	> 24 breaths/min	< 8 breaths/min
Temperature	> 38°C	< 35.5°C

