8.5. Electrocardiograms

Twelve-lead ECGs including PR, QRS, QT, QTcB, QTcF, and RR intervals will be obtained for each participant during the study. Change and percentage change from baseline will be calculated at each postbaseline assessment time. Descriptive statistics will be determined for each ECG parameter.

Incidences of clinically notable ECG abnormalities are defined in [Table 3](#). Participants exhibiting clinically notable ECG abnormalities will be listed with study visit. Abnormal values for participants with alert ECG values, defined as an absolute value outside the defined normal ranges and the percentage change from baseline outside (-25%,25%), will be identified and listed.

When triple ECGs are measured, the average of the 3 ECGs will be used in the summary table, but all 3 of these ECGs will be listed.

Table 3: Criteria for Clinically Notable Electrocardiogram Abnormalities

Parameter	High Threshold	Low Threshold
QTcF	> 460 msec	< 295 msec
QTcB	> 460 msec	< 295 msec
PR	> 220 msec	< 75 msec
QRS	> 120 msec	< 50 msec
QT	> 500 msec	< 300 msec
RR	> 1330 msec	< 600 msec

QTcF = Fridericia correction.

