10.1. Changes to Protocol-Defined Analyses

Not applicable.

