3.4 Vital Signs		
3.4.1	Summary of Systolic Blood Pressure	FAS
3.4.2	Summary of Diastolic Blood Pressure	FAS
3.4.3	Summary of Pulse	FAS
3.4.4	Summary of Respiratory Rate	FAS
3.4.5	Summary of Body Temperature	FAS

Table No.	Title	Population

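### Does the SAP need a participant-count table for clinically notable vital signs, and a different alert rule for temperature?

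*SAP*

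**What the plan says.** Protocol 10.4.2 opens with a general rule for quantitative safety variables, naming laboratory values and vital signs as examples, and continues: "Clinically notable abnormal values will be flagged and tabulated based on predefined criteria". It then takes the data types in turn. Laboratory values are to be graded by CTCAE and tabulated. Vital signs get descriptive statistics and a review for notable values; no form of output is named for that review.

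The SAP makes the same division. For laboratory data, SAP 8.3.1 states: "The incidence of abnormal laboratory values and shift tables relative to baseline will be tabulated". For vital signs, SAP 8.4 gives descriptive summaries by visit, sets limits in Table 2, and states: "The abnormal values for participants exhibiting clinically notable vital sign abnormalities will be listed". It adds a stricter alert tier, also listed, which requires both a value beyond Table 2 and a percentage change from baseline outside the open interval from -25% to 25%. For ECGs, SAP 8.5 states: "Participants exhibiting clinically notable ECG abnormalities will be listed with study visit".

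Appendix A has five vital-sign tables, 3.4.1 to 3.4.5, one value summary per parameter; the last is "Summary of Body Temperature". The listings are 2.9.1 (all values), 2.9.2 (abnormal values) and 2.9.3 (alert values). For ECGs it adds Table 3.5.8, "Summary of Outliers of QT, QTcB, and QTcF Interval Value (ms) From 12-Lead ECG", and Table 3.5.9 on clinically significant abnormality. SAP 10.1, "Changes to Protocol-Defined Analyses", is marked not applicable.

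**The concern.** Read against the general sentence of Protocol 10.4.2, the SAP seems to turn a promised tabulation into a listing without declaring the change. The SAP's vocabulary adds weight to this: it keeps the term clinically notable for vital signs and ECGs, and speaks of laboratory values as abnormal or by CTCAE grade. The general sentence is therefore hard to read as covering laboratory data alone. Vital signs belong to the safety secondary endpoint, yet no planned table states how many participants crossed the SAP's own limits.

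The temperature rule raises a separate worry. If no realistic fever can count as an alert, the temperature part of Listing 2.9.3 will be empty by construction. A reader could take that for reassurance in a trial that names infections among its adverse events of interest.

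**Working it through.** The plan states no figure on this point to reproduce. The check has three parts.

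**1. Which vital-sign outputs are planned**

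| Output | Source | Planned? |
|---|---|---|
| Descriptive summary by visit | SAP 8.4; Tables 3.4.1 to 3.4.5 | Yes |
| Listing of all values | Listing 2.9.1 | Yes |
| Listing of values beyond Table 2 | SAP 8.4; Listing 2.9.2 | Yes |
| Listing of alert values | SAP 8.4; Listing 2.9.3 | Yes |
| Number (%) of participants beyond Table 2 | none | No |

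The missing item concerns the 5 vital-sign parameters. Whether PR, QRS and RR are also uncounted cannot be settled, because the content of Table 3.5.9 depends on shells held in a separate document.

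**2. Can the alert rule be met?**

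Inputs: the Table 2 limits and the 25% condition, both from SAP 8.4. A high alert needs a value of at least 1.25 × baseline; a low alert needs at most 0.75 × baseline. The value must also be beyond Table 2.

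Temperature, for baselines inside the Table 2 limits (35.5 to 38.0°C):

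- High: 1.25 × 35.5 = 44.4°C, up to 1.25 × 38.0 = 47.5°C.
- Low: 0.75 × 35.5 = 26.6°C, up to 0.75 × 38.0 = 28.5°C.
- Assuming a baseline of 36.5°C, a fever of 40°C is a change of 40/36.5 − 1 = +9.6%, well short of 25%.

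For the other parameters, the baseline at which a value just at the high limit would be a 25% rise is limit/1.25:

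- Systolic pressure: 155/1.25 = 124 mmHg.
- Diastolic pressure: 100/1.25 = 80 mmHg.
- Pulse: 100/1.25 = 80 bpm.
- Respiratory rate: 24/1.25 = 19.2 breaths/min.

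A value just over the limit is thus an alert from any baseline up to about these levels. The rule works for those four parameters and fails only for temperature.

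**3. What is lost**

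A temperature above 38°C or below 35.5°C meets the Table 2 criterion alone, so it goes into Listing 2.9.2 whatever the percentage change. Protocol 8.3.3 makes a clinically meaningful abnormal vital sign after the first dose an adverse event, and Protocol 9.5 makes serious infections events of special interest. Neither route uses the alert tier.

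A hand count is light work. Protocol Table 3 schedules vital signs at Weeks 2, 4, 8, 12 and follow-up, while Protocol 4.1 calls Week 2 a laboratory-only visit. That gives 4 or 5 scheduled post-dose values per participant, or 12 × 4 = 48 to 12 × 5 = 60 per parameter before any dropout. Only those beyond Table 2 appear in Listing 2.9.2. Each participant is 1/12 = 8.3 percentage points.

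**The case for a change.** The strongest case for a change is that the general sentence in Protocol 10.4.2 is not withdrawn by the later, softer one on vital signs. SAP 8.1 speaks of replacing summary tables, and here no count table was planned that could be replaced. Listing rows are values, not participants, so a reader must do the counting. The remedy is cheap: one table and one footnote, built from flags the listings already need, and Appendix A treats its list as a guideline that can be altered without an amendment if the nature of the analysis is unaffected.

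Part of this stands. The two documents are not worded alike, no vital-sign count table is planned, and the temperature part of the alert listing will be empty whatever happens.

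The step from there to a departure from the Protocol is weaker. Protocol 10.4.2 tabulates laboratory grades and only reviews vital signs, so the SAP's split is a fair reading of it. The Protocol does not ask for a number and percentage of participants. SAP 8.1 gives few events in few participants as its example of when a listing suits, and a study of about 12 is close to that case. The freedom in Appendix A also cuts the other way: if counts prove useful when the report is written, they can be added without changing the SAP.

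**Conclusion.** No change is called for, because none would bring a gain. What remains is a minor inconsistency of presentation across 5 vital-sign parameters, and an alert tier that does nothing for one of them. The data a count table would show are already planned in Listing 2.9.2, and a footnote on temperature would only point the reader there. Neither would move a threshold, a safety finding, the primary endpoint or the handling of any participant. In a single-arm study with no formal tests, no decision rests on such a count.

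This conclusion assumes that Listing 2.9.2 applies the Table 2 limits to every recorded value, as SAP 8.4 indicates; that baseline temperatures lie within 35.5 to 38.0°C; that enrolment stays near 12; and that whoever writes the report does not present an empty temperature section in Listing 2.9.3 as evidence that no fever occurred.
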